6.1 Visit 1 (baseline, day 0)

Prior to admission to the clinical trial, every patient must be informed in detail on the study. Information takes place in person by the treating doctor and in writing by means of the patient information. Only after all questions of the patient have been answered, he/she will be asked to sign two copies of the declaration of consent and to personally date it. Following this, the patient receives a copy of the patient information/declaration of consent; the second copy is kept in the investigator site file.

Upon visit 1, demographic data (age, sex, weight, size, BMI, side) is recorded. Furthermore, physical examination is carried out, including examination of the range of motion (ROM) of the hallux metatarsophalangeal joint (GZGG) as well as assessment of AOFAS forefoot score by means of the "AOFAS Hallux Metatarsophalangeal-Interphalangeal Scale" questionnaire and the average and maximum VPRS. Women of childbearing age undergo laboratory testing to exclude pregnancy. After final examination of the inclusion and exclusion criteria, the patient is admitted to the study, including his admission to one of the two treatment groups according to randomization as explained above.

6.2 Visit 2 (day 1 – 3)

On day 1, hallux valgus surgery is performed under local anaesthesia, at the end of the surgery the pain catheter (InfiltraLong-Katheter 19G x 420mm, Pajunk Medizintechnologie GmbH) is inserted to allow for continuous wound infiltration with ropivacaine 0.2 % or with physiological saline solution. After surgery, the care-taking nursing staff of the respective ward documents the pain level under continuous wound infiltration and standard pain treatment (see point 5.5) every 4 hours via VPRS. On day 2 (first postsurgical day), the pain catheter is removed in the course of the first routine change of dressing during morning visit (approx. 07.30 a.m.). Under standard pain treatment, the care-taking nursing staff continues to document the pain level every 4 hours via VPRS. On day 3 (second postsurgical day), the patient is discharged from hospital. He/she receives a prescription for the intended pain medication as well as further follow-up appointments in 1 (visit 3), 2 (visit 4) and 6 weeks (visit 5). Occurring AEs or SAEs are recorded in the course of the entire hospital stay.

6.3 Visit 3 (day 7 ± 3)

Routine outpatient wound check. Occurring AEs or SAEs, and the maximum and average pain level (VPRS) are documented.

6.4 Visit 4 (day 14 ± 3)

Routine outpatient suture removal. Occurring AEs or SAEs, and the maximum and average pain level (VPRS) are documented.

6.5 Visit 5 (final visit; day 42 ± 7)

Routine outpatient 6 weeks follow-up including x-ray foot in 2 planes. Occurring AEs or SAEs, and the maximum and average pain level (VPRS) are documented. Furthermore, physical examination is carried out, including examination of the range of motion (ROM) of the hallux metatarsophalangeal joint (GZGG) as well as assessment of AOFAS forefoot score by means of the “AOFAS Hallux Metatarsophalangeal-Interphalangeal Scale” questionnaire. Patient satisfaction is collected by means of VRS.

6.6 Follow-up examinations

After conclusion of the study, the examining doctor decides on further outpatient follow-ups.

6.6.1 Assessment of effectiveness

Effectiveness is assessed by the care-taking nursing staff – which is blinded as regards the therapy group – collecting data concerning the VPRS for pain during the patient's stay in hospital which is repeated every 4 hours. For this, the patient indicates the current pain level on a scale ranging from 0 - 10 (0 meaning no pain, 10 meaning the maximum pain imaginable).

Before surgery and in the course of the postsurgical outpatient follow-ups, the respective care-taking doctor assesses not only the pain level by means of VPRS for pain but also the ROM of the hallux metatarsophalangeal joint. Furthermore, upon visit 1 and 5, AOFAS forefoot score is assessed by means of the „AOFAS Hallux Metatarsophalangeal-Interphalangeal Scale“ question-

naire (see annex) and patient satisfaction is assessed by means of VRS.

6.6.2 Safety assessment

AEs, ARs, UARs and SAEs are recorded during the patient's stay in hospital and during outpatient follow-up examinations. AEs to be expected include in particular wound healing disorders and wound infections.

6.6.3 Radiographic examinations

6 weeks after surgery there is a routine x-ray of the foot in 2 planes in the course of the final follow-up. This is the standard treatment in our department and is thus no examination specific to the study.

6.7 Further treatment of the patients after conclusion of the trial

After conclusion of the study, the examining doctor decides on further outpatient follow-ups.

6.8 Drop-out of patients (drop-out)

Patients may – at any time at their own wish – withdraw from the clinical study prematurely and without giving reasons and without facing any consequences for their future treatment. Furthermore, the investigator may exclude patients from the study for reasons of health risks.

The reason for the patient's drop-out of the study is recorded in the CRF. All patients who drop out of the study have to undergo a final examination (corresponding to visit 5) after 6 weeks, the results of which are documented in the CRF.

6.9 Premature termination of the clinical trial

The sponsor is entitled to prematurely terminate the study due to relevant medical/administrative causes. The reasons for discontinuing the study are documented in detail. Patients who are still under treatment when the trial is cancelled, have to undergo a final examination which is documented in the CRF. If the investigator has ethical concerns regarding the continuation of the study, this has to be reported to the sponsor immediately.

The sponsor is entitled to terminate the clinical trial prematurely, if

- the patient recruitment rate is insufficient,
- serious problems with the quality of the collected data, which cannot be solved, occur,
- unforeseeable circumstances have occurred in the respective trial center which do not allow for the clinical study to be continued,
- early proof is provided that one treatment group is superior or, respectively, inferior to the other treatment group (determined by interim evaluation),
- unjustifiable risks and toxicities have occurred (decision following renewed risk/benefit assessment),
- new scientific findings, which appear when the study is being carried out, do not allow for the study to be continued.

The head of the study may decide on cancelling the study with the sponsor or the protocol committee.

7 Adverse events, adverse reactions

7.1 Definitions

An **Adverse Event (AE)** is any noxious occurrence in a person concerned (study participant) who has been administered an investigational product, and which is not necessarily causally related to this treatment. This may be disorders, clinical signs or symptoms which occur or worsen after the patient has been included in the study.

An **Adverse Reaction (AR)** is any adverse and noxious reaction to an investigational product, regardless of its dose.

An **Unexpected Adverse Reaction (UAR)** is an adverse reaction, the nature or severity of which is not consistent with the available information on the investigational product.

A **Serious Adverse Event (SAE)** or, respectively, **Serious Adverse Reaction (SAR)** is any untoward event or any adverse reaction which

- results in death or
- is life threatening or
- results in persistent or significant disability or incapacity or
- requires inpatient hospitalization or causes prolongation of existing hospitalization or
- results in congenital anomalies or birth defects.

A **suspected unexpected serious adverse reaction** is called **Suspected Unexpected Serious Adverse Reaction (SUSAR)** according to the Clinical Trials Directive (Directive 2001/20/EC).

7.2 Documentation of AEs

All Adverse Events, including intercurrent disorders, are to be documented in the patient's file and subsequently in the CRF.

In case an Adverse Event occurs, the patient is to be observed in any case until the symptoms have disappeared or until the pathological laboratory results have returned to their original values, regardless of the causal relationship between the event and the trial medication. Should a persistent secondary disease result from the Adverse Event, this is to be appropriately documented upon conclusion of the study. All findings and results have to be documented on the respective page for Adverse Events in the patient's file as well as in the CRF. The following information is necessary:

- nature of Adverse Event (sign, symptom or disease)
- differentiation (serious/not serious)
- beginning and end of occurrence
- intensity
- causality to investigational product

- measures as regards the investigational product or actions to restore or ameliorate the patient's well-being.
- outcome of event.

7.3 Documentation of SAEs

For documenting the SAEs, the following points are to be strictly complied with:

- The SAE has to be documented on the respective AE page in the CRF and on the SAE form.
- Every SAE has to be reported, in a way as complete as possible, by the investigator to the sponsor within 24 hours .
- The monitor has to check the investigator's data for completeness and has to ensure that the information included in the SAE report matches the information in the database and in additional data sources.

7.4 Reporting of Adverse Events and Adverse Reactions

All adverse events which occur during the present study which are reported spontaneously or reported after consultation with the doctor or which are observed by the same are to be documented and commented in the case report form. Unexpected adverse events are to be documented in relation to their effect on the risk/benefit situation of the subjects, and are to be reported to the sponsor, to the Clinical Trials Coordination Center (KKS) of the Medical University of Innsbruck as well as to the responsible ethics commission.

Should, from the investigator's point of view, the adverse event observed, regardless of whether it is serious or not, challenge the continuation of the study, the study is to be suspended immediately. Thereafter, the decisions of the responsible parties (Data Safety Monitoring Board, ethics commission, investigator, sponsor) on how to proceed are to be awaited. If the investigator deems the adverse event not relevant in this regard, the other committees mentioned (ethics commission) are free to order the study to be stopped (subsequently decision on continuation or termination of the study). So, in principle, each of the parties mentioned (investigator, ethics commission, sponsor) may issue a study stop. Within a committee, the regulations on taking decisions internally agreed upon, shall apply.

7.4.1 Definitions

See point 7.1

SUSAR criteria:

- The adverse reaction has to be serious.
- A causal relationship between investigational product and adverse reaction must be suspected.
- The adverse reaction has to be unexpected. The definition of unexpectedness of an event is oriented towards the reference safety information.

7.4.2 Duty to report suspected unexpected serious adverse reactions (SUSARs)

The sponsor must notify the ethics commission as well as the Austrian Federal Office for Safety in Health Care (Bundesamt für Gesundheit und Sicherheit, BASG) on SUSARs (additionally noting them in the respective case report form) by means of the official form (including additional narrative brief description, if available anonymized enclosures such as copy of results of an autopsy, etc., and, in the case of an unexpected serious adverse event, comment on the new up-to-date risk/benefit situation for the subject). Adverse reactions which have occurred as part of the same clinical trial at home or abroad are subject to notification (sec. 41 e of the AMG).

Deadlines for notification:

- In case of death or life-threatening reactions: within seven calendar days at the latest; information on further measures is to be transmitted within an additional time limit of eight days.
- All other SUSARs: immediately after they become known, however, within 15 calendar days at the latest.

The obligation to notify BASG of SUSARs begins once all requirements for conducting the study are met (favourable opinion given by the ethics commission and non-prohibition by BASG). The obligation to notify ends upon completion of the respective study in Austria, provided that the national end of study has been reported to the authority (in an informal letter).

Once a year, the sponsor has to transmit an annual safety report (Development Safety Update Report, DSUR pursuant to ICHE2F) with all suspected serious adverse reactions (SSARs) to BASG and to the ethics commission.

8 Documentation

The investigator is responsible to ensure that the trial is conducted in accordance with the GCP guidelines, AMG as well as the study protocol, and that the data is correctly entered into the CRF. All data collected in this study has to be entered into the CRF by persons authorized to do so. This also applies to data belonging to patients who were excluded from trial.

The investigator notes the participation on a special patient identification list. This list enables a later identification of the patients and contains the patient number, the patient's full name, his/her date of birth, and the date of admission to the clinical trial. The patient identification list remains in the trial center after conclusion of the trial. In addition, the participation of the patient in this clinical trial has to be noted in the patient's file (trial medication, patient number/randomization number, start and end of trial).

Furthermore, it has to be ensured that the person who is responsible for documentation in the CRF can be identified. A list with signature and initials of the persons who may make entries in the CRF will be recorded in the investigator site file (ISF) and in the Trial Master File.

8.1 Case report form (CRF)

Any and all patient data and examination results shall be entered into the CRFs (Case Report Forms) specifically created for this study.

The case report forms may only be completed with a **black ballpoint pen**. Corrections are to be made in such a way that old entries remain legible (it is not allowed to use correction products). Corrections are to be signed and dated by the authorized person who makes the corrections. Data which is not available or which has not been collected, has to be clearly marked as such (NA or ND). The reasons to do so should be documented, if necessary.

The investigator ensures that any and all patients' data is entered into the CRFs immediately, legibly, completely, correctly and in accordance with the patients' files.

The monitor serves the completed original pages after they have been checked for plausibility and completeness on the sponsor; a copy remains with the investigator and is stored for 15 years.

8.2 Investigator site file

An investigator site file is made available to the trial center. The investigator stores all those documents which are required for the clinical trial in this file. As part of the monitoring, the investigator site file is checked for up-to-datedness and completeness according to the regulations. After the study has been concluded or cancelled, the investigator site file is to be stored for 15 years.

8.3 Data storage

8.3.1 Obligation of the sponsor to store data

All essential data relating to the clinical trial has to be stored by the sponsor for a duration of 15 years after completion or cancellation of the clinical trial. The sponsor shall archive the data and documents relevant to the trial pursuant to legal provisions.

8.3.2 Obligation of the investigator to store data

Records and documents relating to testing or issuing trial medication (e.g. case report forms, declarations of consent, lists on the medication distribution and other relevant documents) are to be stored by the investigators for at least 15 years.

The medical charts and other original data shall be stored for the longest possible period that the hospital, the institution or the private practice enables.

9 Monitoring and audit

Monitoring and audits are carried out in the context of the clinical trial for the purpose of quality assurance.

9.1 Monitoring

The investigator agrees that the monitor checks data in order to ensure satisfying data collection and compliance with the study protocol.

Furthermore, the investigator agrees to collaborate with the monitor and provide him, whenever necessary, all necessary information. This includes access to all documents relating to the study, including the originals of the patients' files relevant to the study. The task of the investigator covers ensuring that the patients' files are as complete as possible, i.e. recording information on anamnesis, concomitant diseases, admission to the trial, visitor data, examination results, drug issuing as well as Adverse Events. It shall also be made possible for the monitor to check data as well as to compare it with the relevant patients' files pursuant to the SOPs and the ICH GCP guidelines in the predetermined time intervals in order to ensure compliance with the study protocol and continuous recording of data. For that, all original medical findings which are necessary as a source for the data in the database are checked. By signing the declaration of consent, the patient has agreed to such checking.

Further tasks of the monitor include:

- checking whether the trial center complies with the requirements of the clinical trial (patient population, equipment, storage of study materials, etc.)
- instructing the investigator and the study staff on the clinical trial
- checking the investigator site file for completeness and up-to-datedness
- documenting patient status
- source data verification
- checking the prescribed notification of SAEs
- checking proper and safe storage as well as storage life of the trial medication
- counting the trial medication returned (drug accountability), checking compliance.

The monitor shall treat all information as confidential and shall maintain the patients' fundamental right to integrity and protection of their privacy.

9.2 Audit

In order to guarantee that the trial is conducted pursuant to GCP guidelines, internal (e.g. by the sponsor) and external (e.g. by the authorities) audits may be conducted. The auditor is independent vis-à-vis the employees who are involved in the trial.

During the audit, the following points are checked, amongst others:

- conduction of the trial according to the study protocol
- validity of data
- quality of trial pursuant to GCP guidelines.

Following every external audit, the investigator receives an audit confirmation by the auditor. This confirmation must be kept in the investigator site file in order to have it at disposal in case of an inspection by the authorities. The audit report is transmitted to the study sponsor. At the end of the trial, an audit certificate is enclosed to the final report. In addition, authorities may conduct audits and inspections pursuant to the Austrian Medicinal Product Act.

10 Data entry and data management

Study with paper-based documentation

Data is managed and processed by the data manager by means of the software SPSS Statistics (company IBM, Armonk, New York, USA) and Excel (company Microsoft, Redmond, WA, USA).

Data is validated by the programmed range, validity and consistency checks. Additionally, there is a manual/visual check for medical plausibility pursuant to the requirements of GCP. If necessary, queries may occur which are to be transmitted to the respective trial center on special forms. On the basis of the forms, the investigator has to review and answer those discrepancies. These forms are then returned to data management where those discrepancies are corrected in the database accordingly. The forms are stored together with the case report form at the trial center and by data management.

Upon study completion, the database is closed after all entries have been entered and all queries have been resolved. This process is documented.

11 Statistics

11.1 Sample size planning

Statistical planning and analysis takes places under the direction of Mag. [name] of the Institute for experimental orthopaedics.

By using the software G*Power (Franz Faul, University of Kiel, Germany), an a priori sample size analysis is carried out. The following parameters shall be assumed for the calculation of the optimal sample size:

- Primary target variable: average VRS (verbal rating scale; 0-10) for pain
- Clinically-relevant difference: 1
- Number of groups: 2 (same group size)
- Statistical methods:
 - Test family: t-test
 - Statistical test: means; difference between two independent means (groups)
 - Type of power analysis: a priori
- Formulation of hypothesis: two pages
- Effect size: Cohen's $d = 1$ (large effect size)
 - assumed mean difference: 1
 - assumed standard deviation: 1
- Type 1 error: 5 %
- Type 2 error: 20%
- Test power: 80%

- Group size: N1=N2
- Drop-out rate: approx. 10 %

An a priori sample size analysis using the parameters mentioned above, results in a targeted minimal power of 0.80 and with a Cohen's d of 1 (reveals large effects) results in a number of 34 people necessary (17 per group). Considering that the drop-out rate is expected to be at 10 %, the optimal sampling size is 40 feet (20 per group). By means of the sampling size used by us, it should be possible to reveal effects of large size with sufficient power.

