3.4 Number of patients

The study includes a total of 50 patients, 25 of which are in the verum group and 25 of which are in the placebo group.

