5.4 Randomization

Randomization takes place in 2 groups as balanced randomization by means of a computer-generated random number sequence. This random number sequence is generated with the help of the website www.random.org (numbers, random sequence generator). The first 25 results are assigned to the verum group, the other 25 results are assigned to the placebo group. Upon admission to the study, the patients receive at random one of these numbers which are contained in sealed envelopes on which the numbers 1 to 50 are written. The randomization envelope is opened by an independent member of the nursing staff – who is not involved in the further treatment of the patient – several minutes prior to the start of surgery. Such member will fill a 50 ml perfusor syringe with either ropivacaine 0.2 % or physiological saline solution. The patients, surgeons as well as the care-taking nursing staff are blinded as regards the content. The deciphering list will only be opened after conclusion of the last follow-up examination.

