11.2 Randomization

Randomization takes place in 2 groups as balanced randomization by means of a computer-generated random number sequence. This random number sequence is generated with the help of the website www.random.org (numbers, random sequence generator). The first 20 results of this list are assigned to the verum group, the other 20 results are assigned to the placebo group. Upon admission to the study, the patients receive at random one of these numbers which are contained in sealed envelopes on which the numbers 1 to 40 [sic] are written. The randomization envelope is opened by an independent member of the nursing staff – who is not involved in the further treatment of the patient – several minutes prior to the start of surgery. Such member will fill a 50 ml perfusor syringe with either ropivacaine 0.2 % or physiological saline solution. The patients, surgeons as well as the care-taking nursing staff are blinded as regards the content. The deciphering list will only be opened after conclusion of the last follow-up examination.

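### The statistics chapter plans and randomises 40 (20 + 20), the rest of the protocol 50 (25 + 25); nothing derives 50 or says which governs

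*Combined protocol and SAP*

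**What the plan says.** Section 11.1 takes average pain as the target variable and finds that its inputs give "results in a number of 34 people necessary (17 per group"). It then allows for loss ("Considering that the drop-out rate is expected to be at 10" %) and concludes that "the optimal sampling size is 40 feet (20 per group"). Section 11.2 carries this into the allocation: "The first 20 results of this list are assigned to the verum group, the other 20 results are assigned to the placebo group", with "sealed envelopes on which the numbers 1 to 40 [sic] are written".

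Other sections plan a larger trial, each giving part of the picture:

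- Synopsis: a total of 50, nothing more.
- Section 3.4: "The study includes a total of 50 patients, 25 of which are in the verum group", with the other 25 on placebo.
- Section 5.4: "The first 25 results are assigned to the verum group, the other 25 results are assigned to the placebo group", with "sealed envelopes on which the numbers 1 to 50 are written".
- Section 5.8.1: envelopes numbered 1 to 50, without group sizes.

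Sections 5.4 and 11.2 describe the same procedure almost word for word; only the numbers differ. Section 14 explains how changes to the protocol are made but records none.

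**The concern.** The allocation rule fixes each patient's arm and defines the list that is decoded after the last follow-up. With two rules in the operative text, the nurse filling the syringe, the monitor checking compliance and the analyst decoding the arms could each follow a written rule and disagree. Recruitment would be complete at 40 under chapter 11 and ten patients short under section 3.4.

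The sample-size justification is also at stake. Section 11.1 supports 40 only. If 50 is the intended number, ten patients receive a catheter and trial infusion without a calculation behind them, and a reader cannot tell whether 50 reflects a different drop-out rate, a different power or something else.

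**Working it through.** **Inputs, all from section 11.1:** two-sample t-test; type 1 error 5%; power 80%; mean difference 1 and SD 1, so d = 1; equal groups; drop-out about 10%. The hypothesis is described as having two pages, which I read as a mistranslation of two-sided.

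**Formula.** Exact noncentral t, with df = n1 + n2 − 2 and noncentrality d × √(n1·n2/(n1 + n2)). Power is the probability that |t| exceeds the two-sided 5% critical value.

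**Step 1: reproduce 34.** At 16 + 16 (noncentrality √8 = 2.83, df 30) power is 0.781. At 17 + 17 (√8.5 = 2.92, df 32) it is 0.807. The smallest equal groups reaching 0.80 are 17 + 17, so 34 is confirmed. A one-sided test would need only 14 per group, which supports the two-sided reading.

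**Step 2: reproduce 40.** 34/0.9 = 37.8, so 38 (19 per group). Rounding up to 40 is reasonable.

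**Step 3: try to reach 50.**

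| Route | Result |
|---|---|
| 34 evaluable out of 50 | implied drop-out 1 − 34/50 = 32% |
| 40 inflated again by 10% | 44 to 45 |
| Two-sided 2.5% (a split over two primary variables) | 42; 47 to 48 after 10% drop-out |
| Power 90% | 46; 51 to 52 after 10% drop-out |
| 40 with a further 20% loss | 40/0.8 = 50 |

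Only the first and last routes land on 50. The first needs about three times the stated drop-out. The last allows for drop-out twice and uses a rate that the documents do not give. The protocol mentions none of these routes.

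**Step 4: power under each total, d = 1.**

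| Planned | Analysed | Power | d at 80% power |
|---|---|---|---|
| 40 | 20 + 20 (no loss) | 0.869 | 0.909 |
| 40 | 18 + 18 (40 × 0.9 = 36) | 0.830 | 0.961 |
| 50 | 25 + 25 (no loss) | 0.934 | 0.809 |
| 50 | 22 + 23 (50 × 0.9 = 45) | 0.906 | 0.855 |

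**Step 5: compare the allocation rules on one list of 50 positions.**

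| Positions | Section 5.4 | Section 11.2 |
|---|---|---|
| 1 to 20 | verum | verum |
| 21 to 25 | verum | placebo |
| 26 to 40 | placebo | placebo |
| 41 to 50 | placebo | not defined |

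Five positions change arm and ten have no arm under 11.2: 5 + 10 = 15 of 50.

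**The case against.** The best defence is that this is text left over from an earlier plan. Sections 5.4 and 11.2 match apart from the numbers; the dedicated section 3.4 says 50; a sic mark sits beside the 40 in section 11.2 and not beside the 50 in section 5.4; and section 11.1 separates an optimal size from the size actually used. On that reading 50 governs, a single deciphering list exists, and decoding uses that list, not the prose. The 15-position count is then artificial, because no section applies both rules to one list, and no loss of power or bias has been shown.

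Part of this stands. The signs do lean towards 50, and the power of the trial is not in question. The 15 positions show what the two rules say when read literally on one list; they are not a count of misallocated patients. Two separately generated sequences could differ at any position.

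The defence does not remove the defect. The sic mark flags an oddity without resolving it. No section says that 50 governs, and none explains why the trial exceeds the calculated number. Chapter 11, where an auditor or analyst would look, still specifies 40.

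**Conclusion.** The concern holds. The operative text contains two totals that differ by 10 patients and two incompatible allocation rules. Only the 40 can be traced to a calculation; nothing in the text available for review, which lacks some front pages, derives 50 or settles which applies.

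The consequence is for conduct, traceability and the justification of N. It is not a shortage of power: both totals exceed the targeted 0.80 after 10% drop-out. Those power figures rest on d = 1, a two-sided 5% test and loss spread about evenly between arms. They apply to average pain only, because section 11.1 makes no calculation for maximum pain, which section 11.3.1 also lists as primary.

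**What to change.** Adopt one N and one allocation list throughout, and state why that N was chosen.

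- **If 50 stands:** restate section 11.1 as 50 patients (25 + 25), about 45 evaluable after 10% drop-out, power about 0.91 for average pain at d = 1, or 80% power at d of about 0.855. In section 11.2, replace the 20 + 20 text with a reference to the list in section 5.4. No patients are added to the 50 in section 3.4.
- **If 40 stands:** correct the synopsis and sections 3.4, 5.4 and 5.8.1 to 40 (20 + 20, envelopes 1 to 40). With 36 evaluable, power for average pain is about 0.83.

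In either case, change feet to patients in section 11.1, to match the unit used elsewhere.

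The edits are to wording: two sections if 50 stands; the synopsis and three sections if 40 does. Section 14 still requires a change to study procedure to be written, reasoned and signed, with ethics or authority approval where necessary. If a list and envelopes have already been prepared, choosing the other N would also mean remaking them.
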